## **4.6 Study Restrictions**

### **4.6.1 Prohibited Medications**

Subjects will be required to avoid using non-prescription medication (except nicotine-containing substances and acetaminophen up to 2000 mg per day) within 7 days prior to first drug administration and throughout the study, unless in the opinion of the medical monitor, in consultation with the investigator or designee, the product will not interfere with the study procedures or data integrity or compromise the safety of the subject.

Subjects will be required to avoid using prescription medications or natural health products (except vitamin or mineral supplements, acceptable forms of birth control, and hormone replacement) within 14 days prior to first drug administration and throughout the study, unless in the opinion of the investigator or designee, the product will not interfere with the study procedures or data integrity or compromise the safety of the subject.

Concomitant medications are prohibited in this study unless prescribed by the investigator to treat clinical events or exempted by the investigator on a case-by-case basis because they would be unlikely to affect the study results or subject safety (eg, topical medications). All medications taken by subjects after Screening until the completion of the Follow-up visit will be documented

as concomitant medications. The reported medications will be reviewed and evaluated by the investigator to determine if they affect a subject's eligibility or continued participation in the study.

#### **4.6.2 Contraceptive Precautions**

For women of childbearing potential with male sexual partners, examples of medically acceptable forms of contraception are provided in [Table 4](#). Subjects must agree to use medically acceptable contraception for at least 1 month prior to screening (at least 3 months for oral and transdermal contraceptives) and for at least 1 month after last study drug administration. Women must also abstain from ovum donation from screening and for at least 1 month after last study drug administration.

Women of childbearing potential without male sexual partners must be willing to maintain their sexual status (including abstinence) throughout the study.

Women who are not of childbearing potential must be surgically sterile (hysterectomy and/or bilateral oophorectomy/salpingo-oophorectomy, as determined by subject medical history) or congenitally sterile, or must be post-menopausal. Post-menopausal is defined as being amenorrheic for at least 1 year without another cause and a follicle-stimulating hormone (FSH) level  $\geq 26$  IU/L.

**Table 4 Medically Acceptable Forms of Contraception and Duration of Use for Females of Childbearing Potential with Male Partners**

Medically Acceptable Forms of Contraception	Prior to Screening	During the Study
Combined oral pill		
Patch	3 months	
Vaginal ring		Throughout the study. Subjects will be advised to continue using acceptable contraception for at least 1 month after the last study drug administration.
True abstinence		
Intrauterine device or system		
Progestin implant or injection		
Bilateral tubal ligation	1 month	
Double-barrier methods (ie, male condom in addition to a diaphragm, cervical cap, or contraceptive sponge)		

For male subjects with female sexual partners of childbearing potential, examples of medically acceptable forms of contraception include true abstinence, vasectomy, or male condom for subjects plus an additional method of contraception for their female partners.

#### 4.6.3 Dietary and Other Restrictions

In addition to the inclusion and exclusion criteria listed in Section 4.2 and Section 4.3, the subject must agree to abide by each of the following restrictions for the specified time:

- Subjects will be asked to abstain from alcohol for 24 hours prior to each study visit.
- Subjects will be asked to abstain from recreational drug use throughout the study, from Screening until after the last treatment visit.
- Subjects in both Part A and Part B will be required to abstain from smoking for at least 2 hours prior to dosing and at least 15 minutes before each breath alcohol measurement. Subjects in Part A will also be required to abstain from smoking for at least 6 hours after dosing in the Dose Selection Phase. Subjects in Part B will also be required to abstain from smoking for at least 4 hours after dosing in the drug discrimination test and for at least 6 hours after dosing in each Treatment period. Smoking will be permitted at short breaks, at the discretion of the research site staff, at times other than the restricted time intervals described above.
- The use of other nicotine-containing substances (eg, gum, patch, e-cigarettes) is not permitted during inpatient stays at the CRU.
- Subjects in both Part A and Part B will be required to fast (abstain from food) for at least 8 hours prior to dosing and for at least 4 hours post-dosing during the Dose Selection Phase in Part A and during the drug discrimination test and Treatment Phase in Part B. Water will be permitted *ad libitum* except for at least 1 hour prior to dosing and for at least 1 hour post-dosing, with the exception of any liquids administered as part of dosing procedures.
- Subjects will be asked to abstain from the following foods from 1 week prior to the Dose Selection Phase in Part A and Qualification Phase in Part B until after the last treatment visit:
  - grapefruit, pomegranate, pomelo, and star fruit and their juices/products;
  - poppy seeds and Seville oranges and foods containing them (eg, orange marmalade);
  - leafy green portion from vegetables of the mustard green family (eg, kale, broccoli, watercress, collard greens, kohlrabi, Brussels sprouts, mustard greens); however, lettuce and white cabbage are allowed in limited quantities;
  - drinks/foods containing quinine (ie, tonic water).
- Subjects will be asked not to consume more than 450 mg of caffeine per day (eg, approximately 5 cups of tea or 3 cups of regular coffee or 8 cans of cola or 2 energy drinks) from 1 week prior to the Dose Selection Phase in Part A and Qualification Phase in Part B until after the last treatment visit. Subjects will not be permitted to consume caffeine-containing beverages while housed at the research site.
- Subjects will be asked to refrain from driving, operating machinery, or engaging in hazardous activities until they and the investigator are sure the study drug is not impairing their judgment and/or ability to perform skilled tasks. Subjects will be informed that driving under the influence is a criminal offense and that if they are caught driving under the influence, they may be prosecuted to the fullest extent of the law.

- Subjects will be asked to abstain from strenuous physical activity for 48 hours prior to each study visit. Subjects will not be permitted to engage in strenuous exercise during inpatient stays at the research site.
- Subjects will be required to abstain from blood donation during the study and for 30 days after the Follow-up visit.
- Subjects will be required to follow the informed consent form (ICF) and the clinic code of conduct.

#### **4.7    Rescue Medication**

Subjects will receive all standard medical treatment, including administration of rescue medication, should subjects experience severe (Grade 3 or higher) AEs. Standard safety medication (eg, IV naloxone, antihistamine [eg, Benadryl®], epinephrine, solumedrol, ranitidine, advanced cardiac life support [ACLS] rescue medication, etc.) will be administered, if required. If a subject requires treatment for nausea and vomiting, antiemetic medications (eg, ondansetron 4 to 8 mg q8h PO and dimenhydrinate 25 to 75 mg q4-6h PO) may be administered, if not medically contraindicated for the subject.

The principal investigator or designee will be on site during all dosing until at least the continuous oxygen monitoring period is complete (at least 6 hours post-dose in Part A, and at least 4 hours post-dose during the drug discrimination test and at least 6 hours post-dose during each Treatment period in Part B). The investigator or designee will be on-call or on-site thereafter. Dedicated ACLS nurses or paramedics will be assigned to the study during drug administration to monitor AEs and perform safety measures (ie, vital signs).

Subjects will be supervised by staff nurses and paramedics for the duration of the study. In case of emergency or SAEs that require emergency care, the study site is equipped with fully-stocked crash carts, oxygen, suction, and defibrillator. If needed, subjects will be transported to the nearest emergency room to receive more intensive or continuing treatment.

#### **4.8    Subject Discontinuation/Stopping Criteria**

Any subject who voluntarily withdraws consent or is discontinued (eg, because of an AE) from the study prior to completion will be considered as withdrawn from the study. Subjects may be discontinued from the study under any of the following circumstances:

- Occurrence of intolerable AE, as assessed by the investigator or designee
- Clinically significant abnormality on vital signs, ECG, clinical laboratory, or physical examination assessments, as assessed by the investigator or designee
- Withdrawal of consent
- Lost to follow-up
- Administrative reasons (eg, sponsor decision)
- Major violation of the protocol
- If in the opinion of the qualified investigator, it is in the best interest of the subject

- Pregnancy
- Non-compliance with study requirements and restrictions
- Use of a concomitant medication that, in the opinion of the investigator or designee, could interfere with the study procedures or data integrity or compromise the safety of the subject
- Positive urine drug screen at
  - Admission to the Dose Selection Phase in Part A or Qualification Phase in Part B: If a subject presents with a positive urine drug screen at any visit, the urine drug screen may be repeated and/or the subject may be rescheduled at the discretion of the investigator or designee. If benzodiazepines or THC are positive, inclusion will be at the discretion of the investigator, for example, if drug levels are stable at low concentrations or decreasing due to the long half-lives of parent compounds and/or metabolites. THC levels that have increased from the time of the last visit may be acceptable, at the discretion of the investigator or designee, provided that there are no visible signs of impairment and/or intoxication due to THC exposure (eg, euphoria, dry mouth, slowed reflexes, excessive drowsiness, increased appetite, red eyes, paranoia, anxiety, hallucinations, tachycardia, emitting odor of marijuana).
  - Admission to any Treatment Period in Part B: Subjects who have a positive urine drug screen and a COWS score < 5 may be rescheduled at the discretion of the investigator or designee. If benzodiazepines or THC are positive, inclusion will be at the discretion of the investigator, for example, if drug levels are stable at low concentrations or decreasing due to the long half-lives of parent compounds and/or metabolites. THC levels that have increased from the time of the last visit may be acceptable, at the discretion of the investigator or designee, provided that there are no visible signs of impairment and/or intoxication due to THC exposure (eg, euphoria, dry mouth, slowed reflexes, excessive drowsiness, increased appetite, red eyes, paranoia, anxiety, hallucinations, tachycardia, emitting odor of marijuana).
- COWS score  $\geq 5$ . Subjects will be medically managed for at least 4 hours or longer until the investigator determines that the subject can be safely discharged from the CRU.
- Positive breath alcohol test at admission to the Dose Selection Phase in Part A or Qualification Phase or any Treatment Period in Part B. Subjects with a positive result at Screening or admission to any visit may be rescheduled at the discretion of the investigator or designee.
- Termination of the study
- Subject did not meet the qualification criteria outlined in Section 4.5.
- Dose escalation (Part A) has been stopped according to the criteria outlined in Section 4.9.

When an event such as a family emergency, a transient intercurrent illness (such as a cold) unrelated to study drug, or a remediable act of non-compliance prevents a subject from participating in a scheduled visit, but the subject wishes to continue in the study, with the

permission of the sponsor/medical monitor and in consultation with the investigator the research site staff may attempt to reschedule the visit and retain the subject in the study.

If a subject is prematurely discontinued from participation in the study for any reason after study drug administration, the investigator or designee must make every effort to perform the assessments scheduled for the Follow-up visit. The reason for withdrawal will be recorded in the case report form (CRF) and the subject's source medical record.

Replacement subjects may be added at the sponsor's discretion, in agreement with the principal investigator. Each replacement subject will be assigned to the same treatment sequence as the subject who is replaced.

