## 4. STUDY POPULATION

### 4.1 Number of Subjects

In Part A, approximately 5 cohorts of approximately 8 unique subjects per cohort is planned or until the MSD is identified. Additional cohorts may be added, at the sponsor's and investigator's discretion, if additional data at a dose level are needed or if a dose level, intermediate to those

proposed, needs to be considered for safety or tolerability reasons, or a dose higher than those planned is required to be tested, based on supporting safety data.

In Part B, a sufficient number of subjects will participate in the Qualification Phase in order to randomize an estimated 56 subjects into the Treatment Phase, with the intent to complete approximately 42 subjects. Replacement subjects may be added at the sponsor's and investigator's discretion to ensure that sufficient data are collected to meet the main study objectives.

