## **5.3 Method of Assigning Subjects to Treatment Groups**

Randomization will be used to avoid bias in the assignment of subjects to treatment sequences, to increase the likelihood that known and unknown subject attributes (eg, demographics and baseline characteristics) are evenly balanced across treatment groups, and to enhance the validity of statistical comparisons across treatment groups.

Each potential subject will be assigned a unique number (Subject Number) in the screening process. This number will be used to identify the subject throughout the study. Subjects who enter the Treatment Phase will be assigned a unique Randomization Number to identify their sequence of study treatments. Once any subject number is assigned, it cannot be reassigned to any other subject.

All randomization codes will be generated by the sponsor/designated unblinded statistician(s) at INC Research before the start of the study. Sealed code break envelopes will be provided before the start of the study.

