## 5.5 Blinding and Unblinding Procedures

### 5.5.1 Dose Selection Phase (Part A)

For each dosing cohort, an unblinded statistician from INC Research, not otherwise involved in the study, will prepare a list of subject randomization numbers. These randomization numbers will be used to prepare individual subject doses. Sealed qualification code break envelopes will be available for each subject in case of emergency.

Upon completion of each cohort of subjects, the randomization codes for the completed subjects will be unblinded by the CRU pharmacy. After unblinding, the safety data will be reviewed to determine if dosing can proceed for the next planned dosing cohort, as described in Section 4.9.

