### 5.5.3 Treatment Phase (Part B)

The only persons with access to the blinding schema during the Treatment Phase will be the designated pharmacy personnel who are responsible for the dispensing of study drug, the compliance auditor(s) who verify conformity to study procedures, and the unblinded statisticians who generate the code. Under normal circumstances, the blind will not be broken until all subjects have completed all treatments. During the Treatment Phase, blinded dosing information

will be broken only in an emergency where knowledge of dosing information could impact further treatment decisions or aid in the emergency treatment of a subject. Individual blinded dosing information can be broken by opening a subject's sealed code break envelope, thereby, not compromising the blind for the remaining subjects. Individual code breaks by the investigator or designee will result in the withdrawal of the subject from the study. The date, time, and reason for the unblinding will be documented in the appropriate section of the CRF and in the source documents.

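### Part B: a replacement for a subject whose code was broken inherits the disclosed treatment sequence, which can undo the blind for that replacement (minor, nearly free to fix)

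*Protocol*

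**What the plan says.** All of this concerns Part B of the protocol.

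- **Code breaks (Section 5.5.3).** During the Treatment Phase, blinded dosing information "will be broken only in an emergency where knowledge of dosing information could impact further treatment decisions" or help in treating the subject. The section then says: "Individual blinded dosing information can be broken by opening a subject's sealed code break envelope, thereby, not compromising the blind for the remaining subjects". The consequence for the subject is fixed: "Individual code breaks by the investigator or designee will result in the withdrawal of the subject from the study".
- **Replacement (Section 4.8).** "Replacement subjects may be added at the sponsor's discretion, in agreement with the principal investigator". The allocation rule follows at once: "Each replacement subject will be assigned to the same treatment sequence as the subject who is replaced". No exception is made for a subject withdrawn after a code break.
- **Replacement (Section 4.1).** The Part B paragraph also gives the investigator a say: "Replacement subjects may be added at the sponsor's and investigator's discretion".
- **Randomization (Sections 5.3 and 5.3.2).** Subjects entering the Treatment Phase are "assigned a unique Randomization Number to identify their sequence of study treatments". The 14 possible sequences are printed in Table 9.

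The protocol does not say whether an envelope shows one period or the whole sequence. It also does not say whether the site is told which withdrawn subject a replacement number corresponds to. The SAP is limited to Part A (SAP Sections 2.1 and 5) and does not touch the matter.

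**The concern.** Section 5.5.3 assures the reader that opening one envelope leaves everyone else's blind intact. That is true of subjects already randomized, whose sequences are their own. It need not be true of a person recruited later to take over the opened sequence. For that person, whatever the envelope disclosed is information about doses not yet given, and it may be held by the investigator who opened it.

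What is at stake is the investigator's blind for that replacement. The protocol leaves several judgments to the investigator or designee: grading AE intensity (Section 7.2.1), assigning causality (7.2.2), deciding on an ad hoc COWS assessment (6.3.9.2) and deciding on discontinuation (4.8). A replacement who finishes all periods can also enter the Completers population, which keeps subjects regardless of protocol deviations (8.1.1.2) and is the population for the Drug Liking contrasts (8.1.3).

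**Working it through.** **1. The plan's own figures.** Section 8.2 gives a mean difference of 24.6 between hydromorphone 8 mg and placebo, SDs of 18.4 and 18.0, a margin of 11, one-sided alpha 0.05, 42 completers and about 25% dropout.

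- Randomized number: 42 / (1 − 0.25) = 56 = 14 × 4; completers 42 = 14 × 3. Both agree with the protocol.
- Power, by a simple paired calculation. The correlation ρ between a subject's two scores is not given; ρ = 0 is an assumption and the least favourable of the values tried. SD of the difference = √(18.4² + 18.0²) = √662.56 = 25.74. Effect over the margin = 24.6 − 11 = 13.6. Standardized effect = 13.6 / (25.74/√42) = 3.42. Power = Φ(3.42 − 1.645) = 96.2% (95.8% with a t distribution on 41 df).
- With ρ = 0.3 or 0.5 the normal approximation gives 99.3% or 99.9%. The claim of at least 90% is reproduced.

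**2. What a disclosed envelope reveals, from Table 9.** Count the sequences compatible with what was disclosed.

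- *Whole sequence shown:* 1 candidate remains, and all 7 of the replacement's treatments are known.
- *One period shown:* there are 7 periods × 7 treatments = 49 possible disclosures. Each occurs in exactly 2 of the 14 sequences. Example: treatment F in Period 4 occurs only in DECFBGA and AGBFCED.
- *Comparing the 2 candidates:* in all 49 cases they agree only in the disclosed period. In the example the other periods read D or A, E or G, C or B, then B or C, G or E, A or D. So the disclosed period is certain for the replacement, and each of the other six is a choice between two treatments. A guess is right with chance 1/2, against 1/6 when only the one disclosed treatment is ruled out.
- *Two periods shown:* there are 21 pairs of periods × 14 sequences = 294 cases, and each leaves exactly 1 candidate.

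The chance of naming the replacement's sequence is therefore 100% with a full-sequence envelope and 1/2 = 50% with a one-period envelope. It would be 1/14 = 7.1% if the sequence were drawn independently at random from the 14. The first two figures assume that the site knows whom the replacement replaces.

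**3. Size.** One such replacement is 1/42 = 2.4% of completers. The number of code breaks is not given in the documents.

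**4. What it would cost not to replace.** With 41 completers and ρ = 0: 13.6 / (25.74/√41) = 3.38, and power = Φ(3.38 − 1.645), about 96%. On the same calculation, 90% power needs (25.74 × (1.645 + 1.282) / 13.6)² = 30.7, that is 31 completers.

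**The case against.** The strongest reply is that several optional or uncommon events must coincide: an emergency code break by the investigator or designee, a discretionary decision to replace, and site knowledge of the link between the two subjects. That last step is not in the text. Agreeing that replacements may be added is not the same as being told which withdrawn subject a new number corresponds to. Section 5.5.3 confines the blinding schema to pharmacy, compliance auditors and unblinded statisticians. With 14 dropouts planned for (56 − 42), the mapping need not be obvious. The envelope may also show only one period. Same-sequence replacement has a purpose too, since it protects the intended 3 completers per sequence. All of this stands and keeps the point minor. It does not remove it, because the replacement rule is stated without exception and nothing in the protocol requires the link to be concealed.

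Three stronger readings are tempting, and the documents do not support them.

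- **That Part A has the same flaw.** A reader might infer this from "Upon completion of each cohort of subjects, the randomization codes for the completed subjects will be unblinded by the CRU pharmacy". But Part A subjects receive a single dose and have no treatment sequence. Section 4.1 mentions replacement subjects only for Part B. No section describes a replacement added after a cohort is unblinded, and SAP Section 5 reports Part A as completed.
- **That the primary endpoint is directly biased.** Drug Liking is rated by the subject on a computerized scale, and the subject stays blinded under double-dummy dosing. Section 6.1 describes training beforehand and monitoring that assessments are completed properly; it does not describe staff coaching the ratings.
- **That the disclosed treatment would probably be a high-exposure active dose.** The documents say nothing about which treatments would lead to a code break.

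**Conclusion.** The point holds as a minor one, for Part B only. Sections 4.8 and 5.5.3 do not fit together: the assurance about remaining subjects can fail for the one person who is given the opened sequence. How far it fails rests on two things that the documents leave open. The first is whether the site knows whom the replacement replaces, which is inferred from the investigator's part in agreeing to replacements. The second is what the envelope shows. If the link is known, a full-sequence envelope discloses all 7 treatments. A one-period envelope makes one period certain and leaves two possibilities in each of the other six.

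The consequence is small. Each affected subject is about 2.4% of 42 completers, and sample size and power are not in question. What is exposed is mainly the investigator's grading of AEs and their causality, ad hoc COWS and discontinuation decisions for that subject. It is still worth correcting, because SAP Sections 2.1 and 5 say that Part B had not begun and Section 5 says it will go to a new site, so the text can be changed before anyone is dosed.

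**What to change.** Amend the replacement sentence in Section 4.8 so that it agrees with Section 5.5.3:

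- Where the withdrawn subject's code was broken, either do not replace that subject, or draw the replacement's sequence independently from a reserve list held by the unblinded statistician or pharmacy.
- For all replacements, do not disclose to blinded site staff which withdrawn subject the new randomization number corresponds to.

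Same-sequence replacement can stay for every other withdrawal.

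The cost is one or two sentences and a reserve block in the randomization list. The downside is that one sequence may finish one completer short of 3. The planned mixed model already contains sequence and period terms (Section 8.1.3) and accommodates that imbalance.
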